#### Risks/benefits and risk minimisation

Potential risks from xenon:

The known effects of xenon in humans have all been derived from adult anaesthesia studies. Xenon is known to have minimal effects on the strength of the heart contractions or the blood pressure.[37-40] A slight slowing of pulse rate has been seen in some studies - often not statistically significant.

Xenon is analgesic and causes sedation. These might be considered useful properties in a sedated baby on an Intensive Care Unit.

Xenon is a dense gas. Erring on the side of caution we would not use it in this early study in any baby with airway narrowing or similar lung problems, the exclusion criteria reflect this. Note that the use in piglets weighing 1.5 kg and small airways did not display any ventilation/airway problems (Appendix 4). As with other anaesthetic gases it can diffuse into gas filled cavities in the body such as the bowel. This happens only slowly in adults, and more slowly than with other anaesthetic gases such as nitrous oxide, however for this reason it would not be used in any situation where the bowel was obstructed (our xenon inclusion criteria reflect this).

In animal neonatal studies, there have been no side effects and we can document:

- Improved neuroprotection [15]
- Better cardiovascular stability [31]
- No extubation delay (delay coming off the mechanical ventilator) [15]
- No increase in oxygen requirements [15]

Reference:	CH
Issue:	2
Revision:	3
Issue Date:	1 May 2013
Page	21 of 49

From studies using xenon as an anaesthetic in adults, of which there are many, the experience is that xenon has remarkably few side effects and in particular produces minimal haemodynamic disturbance compared to conventional anaesthetics. [37-40]

Because xenon is almost chemically inert, it is eliminated from the body completely unchanged – it is eliminated from body tissues via the circulation and lungs at the end of the procedure. Xenon, although uncommonly used due to its high cost, does therefore have a license for use as an anaesthetic in adults in several countries, including the UK.

In 2010/2011 our group undertook and successfully completed the first human neonatal feasibility/safety study of xenon+cooling, mainly 50% xenon for periods of up to 18hrs. From this study, in terms of safety, we can document:

- It is feasible to give 50% xenon for up to 18h in infants undergoing therapeutic hypothermia [9]
- Only 0.2-0.3L/hour xenon was used with a closed loop xenon breathing system
- A cuffed tube did not adversely affect ease of extubation
- Xenon is sedative and other sedation is needed when xenon is discontinued
- No significant cardiovascular or respiratory changes before, during and after xenon
- In one child with abnormal/immature lungs, xenon did not increase FiO2 requirement.

See Appendix 4

From the perspective of babies who may already be unwell, the main points to note therefore are:

- i) Xenon is not broken down to any “by products” by the metabolism of the body as many other drugs are, as it is an almost chemically “inert” elemental gas.
- ii) Xenon is very free of side-effects in the adult experience, which may be due to this “inert” nature, but perhaps most importantly:
- iii) Xenon is eliminated from the body completely unchanged via the lungs within a few breaths. This means that if there is any problem, unlike the situation with any drug injected into a vein, xenon is a *reversible treatment*, i.e. it can be easily removed completely, rapidly and unchanged from the body at any time. *This ability to reverse application of xenon and rapidly eliminate it unchanged from the patient in the event of any problem is, although unusual, a key factor from the perspective of safety.*

When the xenon is being administered, a special breathing circuit will be connected to the ventilator designed for this purpose. It will be operated by a member of the team who has documented experience running and troubleshooting with this equipment. (see section 4.0).

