#### **Early predictors of outcome**

#### **For the main analysis we will use**

Time to recovery after birth of a normal aEEG [1]

MRI scan before 14 days of life [33, 2]

Peak LDH value within 72h of life [4, 34]

We will also collect data on:

Plasma glucose at birth (in cord blood)

Age in hours after birth when plasma lactate has fallen to 5mmol/L

Different inotropic drugs needed and the total duration in hours of any inotropic support

Number of anticonvulsants given

Amount and duration of sedation (e.g.morphine)

Age at full oral feeds (breast or bottle or tube)

Neonatal hearing screening result before 14 days of life

Clinical examination at birth, at 7 days of age and at discharge including weight and head circumference

Neurodevelopmental follow up is a part of the routine follow up of infants with HIE, Bayley examination at 18 months of age.

Disability will be defined as any of:

Bayley II mental developmental scale (MDI) score less than 70.

Bayley II motor development scale (PDI) score less than 70. MDI and PDI will also be calculated as DQ, developmental score as this allows a larger range of score for those functioning at a low level [35]. Bilateral cortical visual impairments Hearing loss needing amplification > 40 DB.

In addition any Adverse Events will be recorded and criteria have been devised for stopping the study early if necessary. This includes a Data Review Panel to review data when 4 xenon infants have undergone xenon treatment.

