**Cooling + xenon group**  
 Sedate, mechanically ventilate for cooling.  
 Replace tracheal tube with cuffed of same or 0.5mm smaller size.  
 Inflate cuff until seal just achieved.  
 Commence cooling as in cooling-only group.  
 Commence 50% xenon in breathing gas, maintain for 18h, (cooling continuing to total of 72h).

Reference:	CH
Issue:	2
Revision:	3
Issue Date:	1 May 2013
Page	16 of 49

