1. The dose (fraction of xenon in breathing gas) planned for each patient in the xenon+cooling group will be 50%. It will be applied for 18 hours. It will be commenced as soon as is practicable but no later than 5h after birth once all the entry criteria / consent requirements have been met.
2. If a baby is being retrieved from another local hospital to the study centre (Bristol) using the existing Bristol-provided retrieval team and ambulance, AND they have been consented and randomised to receive xenon AND if it is deemed probable that the delay between birth and the start of xenon in Bristol would exceed an interval of 5 hours, then if logically possible an assigned research team member will accompany or meet the retrieval team and commence xenon delivery at the local hospital or during the return transfer of the baby to Bristol.
- 3) Full data sets will be acquired in two groups of 16 patients. The mortality rate in the patients referred for cooling to Bristol is ~25%.
- 4) Cooling will be for 72 hours using the clinically chosen cooling device in both groups, as is current standard practice for cooling.

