### 3.2 Follow Up

#### Short term information and investigations (*before discharge from hospital*):

These are part of routine clinical practice.

1. Survival
2. Duration of hospitalisation
3. Time to full oral feeds, breast or bottle
4. Hypoxic-ischaemic or other injury on MRI scan (standard sequences for this injury) preferably aged 7-12 days of age and Magnetic Resonance Spectroscopy as a part of the MRI examination if available
5. Intracranial or intraventricular haemorrhage (on MRI, CT or ultrasound)
6. Major venous thrombosis (on MRI or ultrasound)
7. Resistance Index (Doppler examination of cerebral blood flow velocities)
8. Amplitude integrated EEG (aEEG) continuously recorded until after rewarming. Assessment of time to normalisation of background activity, seizure occurrence and duration
9. Pulmonary hypertension needing treatment
10. Pulmonary haemorrhage
11. Pneumonia
12. Pulmonary air leak
13. Systemic hypotension needing inotropic support
14. Prolonged blood coagulation time assessed before xenon and at ~24 hours and/or at clinically indicated timepoints
15. Cardiac arrhythmia (not temperature induced low Heart Rate)
16. Thrombocytopenia (platelets <100,000/ul)
17. Culture proven sepsis
18. Necrotising enterocolitis, medical, radiological or surgically proven
19. Plasma markers of global (increased lactate dehydrogenase (LDH)) or cardiac compromise (increased cardiac Troponin T (cTnT))
20. Renal failure treated with dialysis

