#### **Additionally:**

We will do both short-term (14 days) and long-term (18 months survival) follow-up. In cooled babies we have shown that short-term predictors such as MRI at day 8 [2], time to normal aEEG [1] and peak LDH before 72h [4] predict long-term outcome with a positive predictive value of 84%, 92% and 80% respectively. In this study we will be able to examine these predictors for cooled babies receiving xenon treatment. By defining this relationship one can calculate the sample size for a large trial using short-term outcome.

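### Time to a normal aEEG, one of three main-analysis markers, is read through up to 18 h of a sedative gas given in one arm only; it needs post-xenon read-outs as support

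*Protocol*

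**What the plan says.** **The marker.** Under "For the main analysis we will use", Protocol section 2.1 names three early predictors: time from birth to a normal aEEG, MRI before 14 days, and peak LDH within 72 h. Section 3.2 says of MRI, aEEG and LDH, in that order, that in cooled babies they "predict long-term outcome with a positive predictive value of 84%, 92% and 80% respectively". The aEEG figure is thus 92%.

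**The recording.** Section 3.2 (item 8 of the short-term list): "Amplitude integrated EEG (aEEG) continuously recorded until after rewarming". Section 2.2, Endpoint 12, covers background pattern from before xenon until 12 h past the end of cooling.

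**The exposure.** Only the xenon arm receives 50% xenon. Section 3.1 (Clinical management): "It will be applied for 18 hours", and "It will be commenced as soon as is practicable but no later than 5h after birth". The control arm is sedated, ventilated and cooled.

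**The drug.** The Overview calls xenon an anaesthetic gas, and section 3.1 says that it sedates. From the 14-infant feasibility study, section 3.1 reports: "Xenon is sedative and other sedation is needed when xenon is discontinued". The same section says that xenon leaves the body through the lungs in a few breaths. Item 1 of Clinical management says that sedative drugs are not to be changed.

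**The use.** Sections 2.0, 2.1 and 3.3 intend the early predictors to feed the power calculation for a larger trial. Section 3.2 also plans to examine the predictors in infants who receive xenon.

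**The concern.** The marker is read from brain electrical activity, and for part of the measured interval one arm alone breathes a gas that the protocol calls anaesthetic and sedative. Two routes could move the marker without any change in brain recovery. The gas might alter the trace while it is given. Other sedation might also differ between the arms, being lower during xenon or higher after it stops. Randomisation does not remove either route, because allocation determines the exposure.

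The quoted predictive value was shown in cooled babies. Whether an early or late normal trace means the same under xenon is a question of surrogate validity, and this protocol has to answer it before it reads a between-arm difference as neuroprotection. What is at stake is mainly the next trial: a drug effect on the trace would be carried into its assumed effect size.

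**Working it through.** The protocol states no expected value, spread or target difference for the aEEG marker, so there is no figure of its own to reproduce.

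**1. Exposure window.** Inputs from section 3.1: latest start 5 h of age, duration 18 h.
- Latest planned end: 5 + 18 = 23 h of age.
- Share of the 72 h cooling period: 18/72 = 25%.
- An infant not yet normal at 23 h has had the whole exposure inside the measured interval. Because washout is rapid, a direct gas effect is limited to about the first 23 h. After that only a change in other sedation could act.

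**2. Can the planned check settle validity under xenon?** Inputs: 16 xenon infants (section 9.1); poor outcome 39% locally (section 1.2) to 51% (section 3.4).
- Expected poor outcomes: 16 × 0.39 = 6.2 and 16 × 0.51 = 8.2, so about 6 to 8.
- Assumption: about the same number are predictor-positive.
- Exact 95% lower limit when all n predictions are right: 0.025^(1/n). For n = 6 it is 54%; for n = 8 it is 63%.
- With one wrong prediction the lower limits are 36% (5/6) and 47% (7/8).

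So even a perfect result remains compatible with a predictive value far below 92%.

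**3. How large could a direct gas effect be?** This is a worst-case illustration, not an estimate. It rests on four assumptions: no true benefit; lognormal time to normal aEEG with log-SD 0.6 to 0.9; xenon from 5 h to 23 h of age; and every infant who would normalise in that window read as normal only at 23 h. The documents give no median, so a range is shown. For a median m between 5 and 23 h, the median shift is 23 − m in all the cases below; for m of 23 h or more it is zero.

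| Assumed median (h) | Share normalising at 5–23 h | Shift in median (h) | Shift in mean (h) |
|---|---|---|---|
| 12 | 60–79% | 11 | 6.6–8.6 |
| 18 | 53–64% | 5 | 5.3–5.7 |
| 24 | 44–47% | 0 | 3.5–4.1 |
| 36 | 23–29% | 0 | 1.4–2.5 |
| 48 | 11–20% | 0 | 0.6–1.6 |

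The table covers delay only. An apparent advance, if xenon displaced other sedatives, cannot be sized from the protocol.

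**4. Sedation statements side by side.** Clinical management item 1 leaves sedative drugs unchanged. The feasibility findings say that further sedation is required once xenon stops. Drug choice could stay the same while amounts differ between arms, but the protocol does not say so. Sections 2.1 and 3.2 collect the amount and duration of sedation and the number of anticonvulsants; nothing in the protocol links these to the aEEG comparison.

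**The case against.** The strongest reply has four parts.

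- **No evidence of an effect on the trace.** No passage shows that 50% xenon alters the aEEG; the step from sedation to an altered trace is an inference. The appendices with the feasibility data were not available for this check. This stands: size and direction are unknown, and the table above only bounds one scenario.
- **The protocol already treats validity under xenon as a study question.** It also records the trace after xenon and collects sedation data. This stands as far as data collection goes. Step 2 shows that 16 infants cannot answer the question with useful precision.
- **The conclusions do not hang on this marker.** MRI and peak LDH are not read from the trace, prediction rests on a combination, Bayley follow-up is planned at 18 months, and the analysis is descriptive. Section 9.1 puts feasibility of early recruitment first, then the cooled-only group against historical controls; xenon touches neither. This stands and lowers the weight of the point. It does not protect the between-arm hypothesis or the later power calculation.
- **Landmark read-outs commonly belong in a SAP, and fixed-age grades have no cited predictive value.** Both are fair. The issue raised is how the marker, as the protocol defines it, can be interpreted; the place for the extra analysis is open, and it should not displace the marker.

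A reader might infer that the marker is shown to be biased, or that the pilot cannot tell whether recovery differed. The documents do not support this, for the first and third reasons above and because rapid washout limits a direct gas effect to the first day.

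**Conclusion.** The point holds as a limit on interpretation. For infants who would normalise during exposure, or whose other sedation changes because of xenon, time to a normal aEEG cannot separate drug effect from recovery. A between-arm difference, or its absence, may partly reflect the former. The documents give neither size nor direction. Under the worst-case masking assumption the median moves by 11 h if the true median is 12 h and by 5 h if it is 18 h. It does not move if the true median is 24 h or later, when the mean moves by 0.6 to 4.1 h.

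The conclusion rests on the protocol's own account of xenon as anaesthetic and sedative, on exposure in one arm, and on a predictive value established in cooled babies. It is a cheap improvement and not a flaw that invalidates the pilot.

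**What to change.** - Keep time to a normal aEEG as a main marker.
- Add a prespecified supporting analysis of aEEG background grade at the same fixed ages in both arms, after the last planned xenon hour: for example 36 and 48 h. Read 24 h only where xenon has actually ended; section 3.1 allows delivery to be stopped and resumed, so the actual end time should be checked.
- Show sedative and anticonvulsant exposure over the same hours, by arm.
- State that a between-arm aEEG difference will not be interpreted as neuroprotection, or carried into the power calculation for the larger trial, unless the post-xenon read-outs agree.
- Reconcile the two statements on sedation in section 3.1.

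Cost: no new recording, only some further reading of existing traces. Because the fixed-age grades have no cited predictive value, they support the main marker and do not replace it. A reading soon after xenon ends may still carry a sedation difference, which is why later ages and the sedation data are needed.

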#### Potential risks from breathing system:

We are using a new breathing circuit to deliver this gas. This has been developed over many years by a Consultant Anaesthetist who is a co-researcher on this team and world leader on this subject. It has been tested extensively in laboratory neonatal pig simulations of the condition (see section 4.3.1). To minimise risk of any technical problems:

- i) The equipment design is being evaluated for safety by the MHRA. It will be professionally constructed from all medical grade materials.
- ii) The design is such that the xenon system is placed between the standard mechanical ventilator and the baby. This means that if there is any technical problem, the ventilator can be immediately connected directly to the baby and the xenon system removed in one simple intuitive operation.
- iii) The gas composition, in particular oxygen, of the circuit gas will be continuously measured, as will xenon and the end-tidal carbon dioxide (which reflects the arterial value).
- iv) The breathing system has an overpressure release valve in the event of any mishap.

Reference:	CH
Issue:	2
Revision:	3
Issue Date:	1 May 2013
Page	22 of 49

- v) Furthermore if there were any problem due to the xenon gas itself, reconnection directly to the ventilator would also allow all the xenon to be breathed out from the baby within a few breaths, i.e. the xenon treatment is rapidly reversible. Finally:
- vi) The xenon will be delivered by trained personnel who have also been involved with laboratory trials using xenon in animal models
- vii) The possibility of interaction between the xenon gas and the materials of the breathing circuit has been considered. As xenon is chemically "inert" i.e. does not form chemical compounds except in the most extreme circumstances, there is no perceived risk.
- viii) A full risk assessment in accordance with standard medical device regulatory requirements has been undertaken and thoroughly documented

This design of breathing system has now been evaluated in this same patient population as in our recently completed 14 baby human feasibility/safety study. The findings are summarised in Appendix 4.

Use of cuffed tracheal tube:

After onset of cooling and attainment of a stable state, the tracheal tube would be replaced with a cuffed commercially available tracheal tube (Kimberley-Clark microcuff) of the same or 0.5mm smaller size as the existing one.

To minimise the gas pressure in the cuff:

- i) The cuff would be inflated until leakage of gas around the cuff had just ceased audibly and also according to the ventilator monitor.
- ii) This particular tube has a high volume, low pressure cuff and is specifically designed for long term use on the paediatric or neonatal intensive care unit. Publication of a large scale randomised multicentre trial of uncuffed versus modern cuffed tracheal tubes in small children (0-5yrs, n=2246) has recently taken place. The incidence of complications was no greater than that seen with uncuffed tubes. The conclusions were "*The use of cuffed TTs in small children provides a reliably sealed airway at cuff pressures of <or=20 cm H2O, reduces the need for TT exchanges, and does not increase the risk for post-extubation stridor compared with uncuffed TTs.*" [41] (See [Appendix 11](#) for abstract of this paper).
- iii) The cuff pressure will be monitored and recorded at the time of initial inflation, during xenon administration every 2 hours and just prior to final deflation.

N.B. Any Adverse Events such as stridor or failure of extubation secondary to vocal cord, nerve or subglottic damage will be recorded.

In this way any theoretical risk of post-extubation stridor will be minimised. Any such Adverse Events at or around the time of extubation will also be recorded.

Experience with this cuffed tube in neonates with xenon:

In 2010/2011 our group successfully undertook and completed the first human neonatal feasibility/safety study of xenon+cooling, mainly 50% xenon for periods of up to 18hrs. From this study, in terms of safety of the cuffed tube we can document:

- Babies were reintubated with a cuffed tube 0.5mm smaller than the uncuffed tube that had been in place previously. Cuff pressure was measured frequently during the period of xenon delivery and the cuff was deflated post-xenon delivery.
- The target cuff pressure was the lowest cuff pressure we could achieve without there being any gas leakage past the cuff. This was typically 11cm H2O, - much lower than the maximum of 20 cm H2O used in the above randomised tracheal tube study
- We observed stridor post-extubation in 1 of the 14 babies. See [Appendix 11](#).

Further information can be found in Appendix 4.

Cleaning/disinfection:

The entire circuit will be single-use. Between patients, the entire breathing circuit and hoses will be replaced with a fresh item.

Reference:	CH
Issue:	2
Revision:	3
Issue Date:	1 May 2013
Page	23 of 49

### Potential benefit to research participants

The hypothesis is that babies enrolled into the study may derive additional neurological benefit from the xenon/cooling combination exceeding that seen from cooling alone, following the pattern seen in all the *in-vivo* small and large animal studies performed so far.

### 3.2 Follow Up

#### Short term information and investigations (*before discharge from hospital*):

These are part of routine clinical practice.

1. Survival
2. Duration of hospitalisation
3. Time to full oral feeds, breast or bottle
4. Hypoxic-ischaemic or other injury on MRI scan (standard sequences for this injury) preferably aged 7-12 days of age and Magnetic Resonance Spectroscopy as a part of the MRI examination if available
5. Intracranial or intraventricular haemorrhage (on MRI, CT or ultrasound)
6. Major venous thrombosis (on MRI or ultrasound)
7. Resistance Index (Doppler examination of cerebral blood flow velocities)
8. Amplitude integrated EEG (aEEG) continuously recorded until after rewarming. Assessment of time to normalisation of background activity, seizure occurrence and duration
9. Pulmonary hypertension needing treatment
10. Pulmonary haemorrhage
11. Pneumonia
12. Pulmonary air leak
13. Systemic hypotension needing inotropic support
14. Prolonged blood coagulation time assessed before xenon and at ~24 hours and/or at clinically indicated timepoints
15. Cardiac arrhythmia (not temperature induced low Heart Rate)
16. Thrombocytopenia (platelets <100,000/ul)
17. Culture proven sepsis
18. Necrotising enterocolitis, medical, radiological or surgically proven
19. Plasma markers of global (increased lactate dehydrogenase (LDH)) or cardiac compromise (increased cardiac Troponin T (cTnT))
20. Renal failure treated with dialysis

